Appendix Materials

Table 1

Comparison of Parenteral Fat Emulsions

	Intralipid® 20%	Liposyn® II 20%	Omegaven® 10%
Soybean oil	100%	50%	
Safflower oil		50%	
Fish oil			100%

% of Total Fat:

Linoleic acid	50	65	0.1 – 0.7
α-Linolenic acid	9	4	0.2
EPA			1.25 - 2.82
DHA			1.44 - 3.09
Arachidonic acid			0.1 - 0.4
Glycerol	2.3	2.5	2.5
Egg Phospholipid	1.2	1.2	1.2
Total kcals per ml	2.0	2.0	1.12
Available in the U. S.	Yes	Yes	No

Table 2: Schedule for Required Safety Monitoring for Omegaven® Therapy

(To be done baseline pre-Omegaven® therapy and serially as indicated until direct bilirubin <2.0 mg/dL on two serial measurements)

Parameter	Baseline	Every 2 wk to every month
Essential Fatty Acid Profile	X	X (month)
PT	X	X
PTT	X	X
INR	X	X

Table 3: **Suggested** Monitoring Schedule for Omegaven® Therapy

Parameter	Baseline (pre-therapy)	Daily	Every 2 wk to monthly
Body Weight	X	X	
Length; head circumference	X		X
Fluid intake	X	X	
Laboratory tests:			
Sodium, Potassium	X		X
Chloride, Bicarb.	X		X
Glucose	X		X
BUN/Creatinine	X		X
Triglycerides	X		X
Ca, P, Mg	X		X
Albumin	X		X
ALT (SGPT)/AST	X		X
Alk phosphatase	X		X
Fractionated Bilirubin	X		X
GGT	X		X
Cholesterol	X		X
Hemoglobin/Hct	X		X
WBC	X		X
Platelets	X		X
PT	X		X
PTT	X		X
INR	X		X

***For safety purposes:** serum triglycerides, coagulation labs are obtained at baseline, then biweekly for 4 weeks, and monthly thereafter; fatty acid profile is obtained at baseline, then monthly thereafter. Dose reduction will occur if there is evidence of lipid intolerance (serum triglycerides > 200mg/dL) or evidence of bleeding. Growth indices include weight, length, and head circumference will be computed every 2 weeks. Infants receiving Omegaven for more than one month will have vitamin E and copper levels drawn.

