Routine monitoring done at outpatient appointments and at home (through collaboration with the necessary home care agencies) will be recorded. No blood work will be done for study purposes only. Anthropometrics, new diagnoses, surgical procedures, medications, hospital readmissions, infections, feeding plans (e.g., volume, caloric density, and name of enteral formulas), and other pertinent data will also be recorded. The Team physicians will monitor clinically for signs of an essential fatty acid deficiency and adjust the nutrition strategy as needed.

Baseline laboratory monitoring (Table 2 and 3) recorded within 10 days of enrollment will include: BUN, CO₂, creatinine, glucose, serum chloride, potassium, sodium, calcium, phosphorus, magnesium, triglycerides, white blood cell count (WBC or leukocyte count), WBC differential count, red blood cell count (RBC or erythrocyte count), hematocrit (Hct), hemoglobin (Hgb), mean corpuscular volume (MCV), mean corpuscular hemoglobin (MCH), mean corpuscular hemoglobin concentration (MCHC), red cell distribution width (RDW), platelet count, and mean platelet volume (MPV), liver panel [alanine aminotransferase (ALT), aspartate aminotransferase (AST), gamma-glutamyl transferase (GGT), alkaline phosphatase (ALP), albumin, total protein, direct bilirubin (conjugated), total bilirubin, lactic acid dehydrogenase (LDH)], essential fatty acid (EFA) profile, prothrombin time (PT), partial thromboplastin time (PTT), and INR. The above lab monitoring, with the exception of the EFA profile, will typically be done approximately every month at home or at each clinic visit. Routine evaluations done through the home health service will be continued as usual.

Dose Modification

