Lipid Intolerance. If lipid intolerance develops (defined as serum triglyceride levels > 200 mg/dl), the following will be considered prior to reducing the dose: a) if the level was obtained while the patient was receiving a continuous 24 hour infusion of Omegaven®, the total dose should be infused over 20 hours, and a repeat serum triglyceride level obtained prior to resuming the infusion 4 hours later, b) other sources of lipid intolerance should be considered and addressed (drugs, renal disease). If the triglycerides continue to remain high despite the aforementioned interventions, a dosage reduction of 25% of the current dose will be considered. If subsequent triglyceride levels are elevated the dosage will continue to be reduced, and then Omegaven will be discontinued if there is no effect of dose reduction. Subsequent levels will be monitored and adjustments made. After a week, if triglyceride levels are in an appropriate range, Omegaven will be reintroduced.

Duration of Therapy. Patients will remain on Omegaven® until weaned from PN. Patients may continue monotherapy with Omegaven® as an additional source of calories after the dextrose/protein portion of PN is discontinued. Omegaven may be restarted within seven days of discontinuing therapy. After seven days, and meeting inclusion criteria, Omegaven can resume at the initial dose of 0.5 grams/kg/day, advancing to 1 gm/kg/day

Adverse Event Criteria and Reporting Procedures

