Adverse events (AEs) and serious adverse events (SAEs) will be assessed and reported from the time of the first Omegaven® infusion until Omegaven completion and resolution of event(s). This is a very high risk population so adverse events are not uncommon. However, events such as death, blood stream infection, the development or worsening of respiratory distress, or hemodynamic instability; electrolyte abnormalities, catheter malfunction, bowel obstruction, and urinary tract infection will be reported. Any serious or unexpected adverse events will be reported to the SIUH IRB within 48 hours, and the FDA within 7 days. In particular, the patient will be observed during and shortly after Omegaven® administration for the occurrence of anaphylactic or allergic reactions. As inpatients, those experiencing adverse events that are moderate or severe in nature and that may be related to Omegaven® will have their treatment temporarily halted until the adverse event has resolved. Dose modifications will occur as described above. Patients receiving Omegaven® at home will be observed by their parent or caregiver. If adverse events that are moderate or severe in nature as an outpatient, parents will be told to report to the Emergency Department at Staten Island University Hospital for evaluation and possible hospital admission for their child. If a dose reduction is made for adverse events later considered to be unrelated to Omegaven®, the Omegaven® dose will be increased back to the dose prescribed prior to the dose reduction. Patients with anaphylactic or allergic reactions will not continue treatment.

Adverse events and serious adverse events will be collected and reviewed monthly for emerging patterns.

Patients will be withdrawn from Omegaven® treatment for any of the following:

- a) Parent/legal guardian requests to discontinue treatment and/or observation for any reason.
- b) A suitable organ has been located and the patient is able to undergo a liver or liver/intestinal transplant.
- c) Decision by the Principal Investigator that termination is in the patient's best medical interest.
- d) Omegaven will be stopped if lipid intolerance persists despite therapeutic changes as described on page 3 of the protocol (see Dose Modification).
- e) Omegaven will be stopped if essential fatty acid levels are below normal two serial measurements.

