The infusion of Omegaven® can lead to a prolonged bleeding time and an inhibited platelet aggregation. In rare cases, patients may experience a fishy taste. The administration of Omegaven® should be stopped or reduced if there is a marked increased in blood glucose levels during the Omegaven® infusion. Undesirable effects that are seen during the infusion of Omegaven® that may also occur with conventional fat emulsions (i.e., Intralipid®) include slight rise in body temperature, flushing or cyanosis, vomiting, changes in blood pressure, erythema, anaphylactic reactions.

Overdose:

In the event of an overdose of Omegaven® there is a risk of developing fat overload syndrome that may occur when the triglyceride level rises >200 mg/dL acutely as a result of too rapid a rate of infusion, or chronically at high infusion rates in associated with a change in the patient's clinical condition (e.g., renal dysfunction, sepsis). In such cases, the infusion should be stopped or, if necessary, continued at a reduced dose. Metabolic acidosis has occurred in patients receiving Omegaven® at excessive doses without simultaneous administration of dextrose.

Potential Benefit of Omegaven® Treatment

Omegaven® may be effective in stabilizing or reversing hepatic injury associated with the use of parenteral nutrition. It may allow the patient to continue to receive the majority of his/her caloric intake from parenteral nutrition while advancing on enteral nutrition or awaiting liver or liver/intestinal transplant.

Outcome Variables

Laboratory measurements, growth indices and trends will be reviewed as per the suggested monitoring schedule during Omegaven therapy. Desired endpoint to support effectiveness will be evidenced by a decline in serum direct bilirubin levels below 2 on two serial measures.

Potential Risks of No Treatment

Since Omegaven® will only be offered to those patients for whom no standard therapy is likely to be safe and effective, the risks of not being treated are those allowing for the natural history of their disease and associated clinical manifestations to progress. These include fulminate liver failure and death.

Data Safety and Monitoring Plan

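### The required safety schedule ends essential fatty acid testing at bilirubin response, although Omegaven continues and a withdrawal rule still depends on the measured levels

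*Protocol*

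**What the plan says.** The Protocol deals with EFA testing and its use in several places.

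- **Appendix, Table 2.** The title is "Table 2: Schedule for Required Safety Monitoring for Omegaven® Therapy". It lists the EFA profile (monthly), PT, PTT and INR, to be done at baseline and then "serially as indicated until direct bilirubin <2.0 mg/dL on two serial measurements".
- **Appendix, safety note under Table 3.** "fatty acid profile is obtained at baseline, then monthly thereafter". No end and no bilirubin condition is given. Table 3 itself, headed as a suggested schedule, has no EFA row.
- **Outpatient Monitoring and Administration.** The baseline laboratory list includes the EFA profile. The follow-up tests, "with the exception of the EFA profile, will typically be done approximately every month". Physicians are also to watch clinically for signs of deficiency.
- **Adverse Event Criteria and Reporting Procedures, withdrawal rule (e).** "Omegaven will be stopped if essential fatty acid levels are below normal two serial measurements".
- **Duration of Therapy.** "Patients will remain on Omegaven® until weaned from PN". In addition, "Patients may continue monotherapy with Omegaven® as an additional source of calories" once the dextrose/protein part of PN has stopped. Preliminary Studies states that treatment has no maximum duration.
- **Outcome Variables.** The sign of effectiveness is a "decline in serum direct bilirubin levels below 2 on two serial measures".

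**The concern.** The event that ends required EFA testing is the event that defines treatment success. Success does not end treatment, so a responder who still needs PN stays on Omegaven, possibly for a long time and possibly as the only intravenous fat source. Rule (e) still applies to that patient, and it can act only on measured levels.

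The risk is one the Protocol recognises. Table 1 lists linoleic acid at 0.1–0.7 for Omegaven against 50 and 65 for the two soybean-containing products, the dose is capped at 1 g/kg/day, and deficiency is given its own withdrawal rule. If the required table is followed as written, that rule loses its scheduled data in the patients who do best and remain exposed. If the note is followed, the rule works throughout. The Protocol does not say which applies.

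**Working it through.** The Protocol states no figure to reproduce here, so the check sets the texts side by side for one patient: two direct bilirubin values below 2.0 mg/dL, still on Omegaven.

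| Text | Is an EFA profile scheduled after response? |
|---|---|
| Table 2 (required) | No; the until-clause has been met |
| Table 3 (suggested) | No EFA row, before or after response |
| Outpatient monitoring text | EFA excepted from the roughly monthly tests; no schedule of its own given |
| Safety note under Table 3 | Yes, monthly, no end stated |
| Withdrawal rule (e) | Sets no schedule, but needs two successive results |

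**Is response the end of exposure?** No. The Table 2 stop and the Outcome Variables endpoint are the same criterion. Duration of Therapy ties the end of treatment to weaning from PN and allows Omegaven beyond that.

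**Scheduled profiles after response.** Let m be the further months on Omegaven. The Protocol does not give m, so the values are assumed.

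- Table 2: 0 × m = 0.
- Note: 1 × m.

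| m (assumed) | Table 2 | Note | Needed by rule (e) |
|---|---|---|---|
| 3 | 0 | 3 | 2 |
| 6 | 0 | 6 | 2 |
| 12 | 0 | 12 | 2 |

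**An outer marker from the Protocol's own background.** Preliminary Studies cites bilirubin normalising by 9 weeks in one cohort and, separately, several children treated for over 2 years. Combining these as 9 weeks to response and 104 weeks of treatment leaves 104 − 9 = 95 weeks, or 95 × 12/52 = 21.9 months. That is about 21 complete monthly profiles under the note and none under Table 2. Before response, 9 × 12/52 = 2.1 months allows about two profiles after baseline. The two figures come from different patients at another centre, so this marks how far the gap could extend and is not an estimate.

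**A consequence for rule (e).** Because it needs two successive low results, a patient whose last profile before response is the first low one has no scheduled confirmatory profile under Table 2.

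**Coagulation tests.** PT, PTT and INR share the Table 2 stop, but the outpatient text, Table 3 and the note all continue them. That part is minor.

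**The case against.** The best defence is that the texts can be followed together. Table 2 can be read as a minimum up to response that does not forbid later testing, and a team that draws a monthly EFA profile throughout treatment complies with everything. This is correct, and it limits the finding: the Protocol does not prevent safe practice. It does not remove the problem. The only text that continues the profile sits under a schedule headed as suggested, so its binding force is unclear, while the required schedule states an end. The phrase about testing as indicated loosens the frequency but not the until-clause.

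The outpatient exception is weaker evidence than it first appears. It may mean only that EFA has its own monthly schedule while other tests follow clinic visits, and it applies equally before and after response. That stands. The exception does not show that testing stops at response; it only fails to resolve the conflict. The missing EFA row in Table 3 is likewise not specific to the period after response.

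There are other safeguards. Physicians watch for clinical deficiency and may adjust nutrition, and rule (c) lets the principal investigator stop treatment in the patient's interest. These are real, but neither triggers rule (e), which is written on measured levels.

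It is also fair to say that the months used above are assumed, that one hospital and one team run the Protocol so inconsistency between sites is not the issue, and that no endpoint or analysis changes.

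**Conclusion.** The concern holds. The required schedule uses the wrong stop condition for the EFA profile: it ends at the efficacy endpoint when it should end with exposure. The note under Table 3 contradicts it, and nothing in the Protocol decides between them. For a responder still on Omegaven the difference is 0 against 1 scheduled profile per month, under a mandatory rule that needs two results. How many patient-months are affected cannot be derived from the Protocol.

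The conclusion rests on reading the until-clause in Table 2 as an end to required testing, and on some patients responding before they are weaned from PN, which Duration of Therapy allows for. It should be fixed because it bears on patient safety and on whether a stated stopping rule can operate. It has no bearing on the bilirubin endpoint.

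**What to change.** Make two wording edits.

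1. In the Table 2 heading, replace the bilirubin stop with a stop at discontinuation of Omegaven. This also settles the smaller conflict for PT, PTT and INR.
2. In the outpatient monitoring text, replace the bare EFA exception with a statement that the EFA profile is obtained monthly while the patient is on Omegaven, in line with the note.

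The cost is a short protocol amendment. No test is added beyond what the safety note already describes.
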